## 3. STUDY DESIGN

This is a prospective and retrospective multicenter observational cohort study. No additional clinical interventions, experimental drugs or medical devices are applied to enrolled participants. Only routine standard-of-care clinical data, imaging data and pathological data are collected and analyzed.

The study population consists of two cohorts: a retrospective historical cohort and a

prospective newly enrolled cohort. All eligible participants receive standardized preoperative mpMRI and TRUS examinations, followed by clinically indicated prostate biopsy or radical prostatectomy with definitive pathological diagnosis.

All collected high-quality multicenter data are applied for model construction, spatial registration, multimodal feature fusion, model training, internal cross-validation and external multicenter independent validation.

## 4. STUDY POPULATION AND ELIGIBILITY CRITERIA

**Study Population:** Consecutive male subjects aged 40 to 90 years with suspected prostate cancer who complete standard preoperative mpMRI and TRUS examinations and receive subsequent prostate biopsy or radical prostatectomy with complete pathological diagnosis. The population includes retrospective historical cases and prospective newly enrolled cases with complete clinical, imaging and pathological data.

**Inclusion Criteria:** (1) Male subjects aged 40 to 90 years; (2) Subjects scheduled for or having undergone prostate biopsy or radical prostatectomy; (3) Subjects completing standard preoperative mpMRI and TRUS examinations; (4) Subjects with complete postoperative pathological results including Gleason score and ISUP grading; (5) Prospective participants providing valid written informed consent.

**Exclusion Criteria:** (1) Subjects with a history of pelvic radiation therapy or prior radical prostatectomy; (2) Subjects with incomplete or low-quality mpMRI or TRUS images with motion artifacts, missing sequences or unrecognizable lesions; (3) Subjects with concurrent other primary malignant tumors; (4) Subjects with severe systemic diseases interfering with prostate lesion evaluation; (5) Subjects with incomplete clinical, imaging or pathological data; (6) Subjects with MRI contraindications including incompatible metallic implants and severe claustrophobia.

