## 1. STUDY BACKGROUND AND RATIONALE

Prostate cancer is one of the most common malignant tumors in elderly males globally. Clinically significant prostate cancer (csPCa) is closely correlated with tumor progression, distant metastasis and cancer-related mortality. Accurate preoperative identification and risk stratification of csPCa remain major clinical challenges.

Multiparametric magnetic resonance imaging (mpMRI) and transrectal ultrasound (TRUS) are standard preoperative imaging modalities for patients with suspected prostate cancer. The PI-RADS v2.1 scoring system is widely adopted for lesion risk evaluation in clinical practice. Nevertheless, conventional imaging assessment fails

to fully reflect microscopic pathological heterogeneity, thereby resulting in frequent unnecessary prostate biopsies, inconsistent diagnostic accuracy, and potential overdiagnosis or underdiagnosis.

Digital whole-slide images (WSI) of pathological specimens provide high-resolution microscopic pathological features and serve as the diagnostic gold standard for prostate cancer. Spatial inconsistency between macroscopic imaging lesions and microscopic pathological changes restricts precise correlation of imaging manifestations with pathological grading results.

Artificial intelligence and deep learning techniques support high-throughput feature extraction and multimodal data fusion. Spatial registration algorithms enable accurate alignment between preoperative imaging lesions and postoperative microscopic pathological structures, which facilitates the construction of precise and interpretable diagnostic models for prostate cancer.

This multicenter observational study is designed to establish and validate a multimodal deep learning prediction model based on spatial registration of mpMRI, TRUS and digital pathological WSI. The model is intended to achieve non-invasive and accurate prediction of csPCa, standardize non-invasive risk stratification, reduce unnecessary prostate biopsy procedures, and provide evidence for optimizing clinical diagnostic and therapeutic decision-making.

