## 2. STUDY OBJECTIVES

**Primary Objective:** To construct and validate a transformer-based multimodal deep learning model for the prediction of clinically significant prostate cancer using spatially registered multimodal imaging and digital pathology data. The area under the receiver operating characteristic curve (AUC) is applied to evaluate the diagnostic discriminative ability of the model.

**Secondary Objectives:** (1) To analyze the spatial correlation between macroscopic imaging characteristics and microscopic pathological heterogeneity of prostate lesions; (2) To validate the generalization performance of the model through internal cross-validation, external multicenter independent validation and international public dataset validation; (3) To evaluate the clinical application value and net clinical benefit of the model via decision curve analysis and clinical impact curve analysis; (4) To verify the clinical value of the model in optimizing prostate biopsy strategies, reducing unnecessary puncture and overtreatment, and improving early precise diagnosis and risk stratification of prostate cancer.

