## 5. DATA COLLECTION

Collected clinical data include age, BMI, PSA-related serological indicators and PI-RADS v2.1 scoring results. Imaging data cover preoperative mpMRI and TRUS images. Pathological data include digital whole-slide images of prostate biopsy or radical prostatectomy specimens, corresponding Gleason score and ISUP grading results. All data are fully de-identified to guarantee participant privacy and data security.

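### Inclusion criterion 4 requires a Gleason score and ISUP grade, so read literally it excludes men with benign pathology and contradicts the stated population of men with suspected cancer

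*Protocol*

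**What the plan says.** Section 4 describes two populations that do not match.

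- The population paragraph recruits "Consecutive male subjects aged 40 to 90 years with suspected prostate cancer" who "receive subsequent prostate biopsy or radical prostatectomy with complete pathological diagnosis". Section 3 uses similar terms: imaging is "followed by clinically indicated prostate biopsy or radical prostatectomy with definitive pathological diagnosis". Neither passage asks for a grade.
- Inclusion 4 then requires "Subjects with complete postoperative pathological results including Gleason score and ISUP grading", and exclusion 5 removes "Subjects with incomplete clinical, imaging or pathological data".
- Section 5 lists, besides the slide images, only "corresponding Gleason score and ISUP grading results" as pathology results. No section mentions a benign or cancer-negative result.

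On purpose, Section 1 wants the model to "reduce unnecessary prostate biopsy procedures". Secondary objective 4 in Section 2 repeats this as "reducing unnecessary puncture and overtreatment". Secondary objective 3 and Section 6 plan decision curves and clinical impact curves. The primary outcome in Section 7 is the AUC for clinically significant prostate cancer (csPCa).

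**The concern.** A man whose biopsy shows no cancer has no Gleason score and no ISUP grade. Under inclusion 4 he lacks a required item, and exclusion 5 gives a second reason to drop him. Yet he is the clearest case of a biopsy that a good pre-biopsy model would have spared.

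If he is dropped, a patient-level AUC compares higher-grade with lower-grade cancer among men already known to have cancer. The planned use is to separate csPCa from everything else among men under suspicion. Prevalence, net benefit and the count of avoidable biopsies would all describe the wrong group.

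The ambiguity also matters in itself. The study is multicentre and draws partly on historical records. If one centre drops benign cases and another keeps them, case mix differs between centres for reasons unrelated to their patients, and the external validation is confounded.

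**Working it through.** **The texts side by side.** Would a man with a benign biopsy and complete imaging qualify?

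- Section 4, population paragraph: yes, since a benign report is a complete diagnosis.
- Section 3: yes, since a benign report is a definitive diagnosis.
- Section 4, inclusion 4: no, since there is no Gleason score or ISUP grade.
- Section 4, exclusion 5: excluded, if the missing grade counts as incomplete pathology.
- Section 5: no benign result is named among the pathology data.

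The same man is therefore in the study under two provisions and out under at least one.

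**Size, as an illustration only.** The protocol gives no case mix, no prevalence and no grade threshold for csPCa, so there is no figure of its own to reproduce. Assumed inputs are a benign share b of 30-55%, an ISUP 1 share g of 10-25%, and the remainder c = 1 - b - g csPCa (ISUP 2 or higher). The analysis is taken as one result per patient.

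- Share of csPCa-negative men lost = b / (b + g)
- Prevalence of csPCa if only graded cancers enter = c / (1 - b)

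| Benign / ISUP 1 / csPCa (%) | Negatives lost | Prevalence, all men | Prevalence, graded only |
|---|---|---|---|
| 30 / 25 / 45 | 30/55 = 55% | 45% | 45/70 = 64% |
| 30 / 15 / 55 | 30/45 = 67% | 55% | 55/70 = 79% |
| 35 / 20 / 45 | 35/55 = 64% | 45% | 45/65 = 69% |
| 40 / 20 / 40 | 40/60 = 67% | 40% | 40/60 = 67% |
| 45 / 15 / 40 | 45/60 = 75% | 40% | 40/55 = 73% |
| 50 / 10 / 40 | 50/60 = 83% | 40% | 40/50 = 80% |
| 50 / 20 / 30 | 50/70 = 71% | 30% | 30/50 = 60% |
| 55 / 15 / 30 | 55/70 = 79% | 30% | 30/45 = 67% |

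**Net benefit.** For a policy of biopsying everyone at threshold t, net benefit = p - (1 - p) × t/(1 - t). With an assumed t of 10% and the 40/20/40 mix, it is 0.40 - 0.60/9 = 0.333 among all men and 0.667 - 0.333/9 = 0.630 among graded cancers. The reference line of the decision curve moves before the model is considered.

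**AUC.** The AUC among all men is a weighted mean of the AUC against benign men and the AUC against ISUP 1 men: (b × AUC_benign + g × AUC_ISUP1) / (b + g). The graded-only AUC is AUC_ISUP1 alone. Two assumed settings:

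- Separations of 1.6 SD (benign) and 1.0 SD (ISUP 1), with AUC = Φ(d/√2), give 0.82-0.85 over the mixes against 0.76 graded only.
- AUCs of 0.88 and 0.72 in the 45/15/40 mix give (0.45 × 0.88 + 0.15 × 0.72)/0.60 = 0.84 against 0.72.

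The fall is about 0.06 to 0.12, driven entirely by the assumed separations. Even its direction requires benign cases to be easier to separate than ISUP 1.

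**The case against.** The strongest reply is that this is a drafting slip. The population paragraph and Section 3 both fit a benign report, and inclusion 4 can be read as listing what a complete report contains when cancer is found. This stands as a point about intent: the protocol does not show that the sponsor means to exclude benign cases or that centres will do so. It does not remove the contradiction, because inclusion 4 is the rule that centres screen against and nothing in the document says a benign result is enough.

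A second reply is that the unit of analysis is not stated. Section 6 speaks of registering lesions to slides. If prediction is by lesion or region, benign tissue within graded patients could supply negatives. This also stands, so the consequences above are tied to a patient-level analysis.

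Stronger readings are tempting but not supported:

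- A reader might infer that unnecessary biopsies cannot be studied at all. Men with low-grade cancer remain eligible. With an ISUP 2 cut-off they are csPCa-negative, and 17-45% of negatives remain in the mixes shown.
- A reader might infer a specific reported AUC. The inputs are assumed, and the case mix of the public datasets is not described.
- A reader might add calibration to the harms. The protocol plans no calibration analysis.

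**Conclusion.** The point holds as a contradiction in the eligibility text. Inclusion 4, backed by exclusion 5 and echoed in Section 5, literally excludes men with benign pathology. The population paragraph, Section 3 and the net-benefit and biopsy-sparing objectives all need them.

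For a patient-level analysis with an ISUP 2 cut-off and 30-55% benign biopsies, all of them assumptions, the literal rule would remove roughly 55-83% of csPCa-negative men and raise prevalence from about 30-55% to 60-80%. The loss of negatives and the rise in prevalence need no assumption about model performance. The AUC change does, and should not be quoted as one value.

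It should be settled in the protocol while the study is recruiting. An analysis plan cannot restore men who were never enrolled.

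**What to change.** Amend as follows.

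1. Inclusion 4: require a definitive histopathological result, either benign or cancer with Gleason score and ISUP grade.
2. Exclusion 5: state that a benign result counts as complete pathology.
3. Section 5: add a benign result to the pathology data collected.
4. State that benign results belong to the csPCa-negative class.
5. Exclusion 2: it lists lesions that cannot be recognised among the image-quality failings. Clarify that this concerns image quality and not the absence of a visible lesion. Otherwise men with nothing visible on imaging could still be dropped after inclusion 4 is repaired.

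The cost is a short amendment to Sections 4 and 5. The men concerned already have mpMRI, TRUS and a tissue diagnosis, so no new patient procedure is needed. Some extra work follows: benign specimens also need whole-slide images and processing, and any centre that has applied the literal rule would have to go back to the men it dropped.

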## 7. OUTCOME MEASURES

**Primary Outcome Measure:** AUC of the multimodal deep learning model for predicting clinically significant prostate cancer at the time of baseline imaging and pathological data collection.

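### Exclusion 2, as worded, can remove men with technically adequate images but no recognizable lesion, which would narrow the study's own cohorts to visible lesions and bias its accuracy estimates

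*Protocol*

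**What the plan says.** Protocol section 4 describes the population as "Consecutive male subjects aged 40 to 90 years with suspected prostate cancer who complete standard preoperative mpMRI and TRUS examinations" and who then have biopsy or prostatectomy. Neither a visible lesion nor a minimum PI-RADS score is required for entry; section 5 lists PI-RADS only as a collected variable.

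Exclusion 2 in the same section removes "Subjects with incomplete or low-quality mpMRI or TRUS images with motion artifacts, missing sequences or unrecognizable lesions". The final ground is not defined, and nothing in the protocol says whether men with adequate images and no visible lesion are kept.

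Section 3 sends the same data to every step: "All collected high-quality multicenter data are applied for model construction, spatial registration, multimodal feature fusion, model training, internal cross-validation and external multicenter independent validation". Section 6 describes registration as the alignment of imaging lesions with the digital slides. Section 7 makes the primary outcome the "AUC of the multimodal deep learning model for predicting clinically significant prostate cancer". The secondary objectives in section 2 include decision-curve net benefit and "optimizing prostate biopsy strategies, reducing unnecessary puncture and overtreatment".

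**The concern.** Motion artifact and a missing sequence are faults of the scan. Whether a lesion can be recognized is a finding on the scan, and it is related to whether the man has clinically significant cancer (csPCa). Placing it among quality grounds lets image content decide who is analysed.

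Two groups could leave. One is men with csPCa that imaging does not show, whom an imaging model is likely to miss. The other is men without csPCa and without a lesion, in whom a biopsy might be avoided. Both matter to a model meant to inform the biopsy decision. Because the criterion names mpMRI or TRUS, a man with a clear MRI lesion that TRUS does not show could also go.

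The wording has two plausible readings that give different populations. Sites screening retrospective records could apply it differently, and the reported performance would then describe a mixture that nobody specified.

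**Working it through.** The protocol gives no AUC target, prevalence, sensitivity or share of lesion-free scans, so there is no figure to reproduce. All inputs below are assumptions. They show direction and plausible size only, and they apply if the exclusion is used to remove men without a recognizable lesion.

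**1. Sensitivity at a fixed threshold.** Let q be the share of csPCa without a recognizable lesion and s the model's sensitivity in those men. Assume sensitivity 0.92 in visible csPCa, which is what the restricted study would report.

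Full-population sensitivity = (1 − q) × 0.92 + q × s.

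With s = 0.30:
- q = 0.05: 0.874 + 0.015 = 0.889
- q = 0.10: 0.828 + 0.030 = 0.858
- q = 0.15: 0.782 + 0.045 = 0.827

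Misses per 100 csPCa are about 11, 14 and 17, against 8 in the restricted set. Over s = 0.2 to 0.5 and q = 0.05 to 0.15, the extremes are 0.782 + 0.030 = 0.812 and 0.874 + 0.025 = 0.899. The overstatement requires only that s is below the sensitivity in visible lesions.

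**2. Specificity at the same threshold.** Let u be the share of men without csPCa who have a recognizable lesion. Assume specificity 0.45 in them and 0.95 in lesion-free men.

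Full-population specificity = u × 0.45 + (1 − u) × 0.95.
- u = 0.4: 0.180 + 0.570 = 0.75
- u = 0.6: 0.270 + 0.380 = 0.65
- u = 0.8: 0.360 + 0.190 = 0.55

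The restricted study would report 0.45, so specificity is understated.

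**3. AUC, the primary outcome.** Let v = 1 − q be the share of csPCa with a recognizable lesion. Pairing every man with csPCa with every man without gives the exact decomposition

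AUC(full) = v·u·A_vv + v(1 − u)·A_vi + (1 − v)·u·A_iv + (1 − v)(1 − u)·A_ii,

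where the first index is the man with csPCa, the second the man without, v means visible lesion and i means none. The restricted study reports A_vv.

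Assume A_vv = 0.80, A_vi = 0.95, A_iv = 0.30 and A_ii = 0.60:
- v = 0.8, u = 0.8: 0.512 + 0.152 + 0.048 + 0.024 = 0.736. Reported 0.80, overstated by 0.064.
- v = 0.9, u = 0.6: 0.432 + 0.342 + 0.018 + 0.024 = 0.816. Reported 0.80, understated by 0.016.
- v = 0.95, u = 0.4: 0.304 + 0.5415 + 0.006 + 0.018 = 0.870. Reported 0.80, understated by 0.070.

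Two further assumed sets were also run: A_vv, A_vi, A_iv, A_ii = 0.85, 0.97, 0.35, 0.60 and 0.75, 0.95, 0.25, 0.55. Across all three sets, with v = 0.80 to 0.95 and u = 0.4 to 0.8, reported minus full AUC runs from −0.098 to +0.071. If only invisible csPCa is lost (u = 1), AUC is overstated by 0.025 (v = 0.95) to 0.100 (v = 0.80). If only lesion-free men without csPCa are lost (v = 1, u = 0.4 to 0.8), it is understated by 0.024 to 0.120. The sign depends on the mix.

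**The case against.** The strongest reply is grammatical. The disputed phrase qualifies incomplete or low-quality images, so it may mean only a lesion that cannot be read because the scan is poor. With no visible-lesion requirement and no PI-RADS threshold, a reader who concludes that all MRI-negative men and all MRI-invisible cancers are removed goes beyond the text. This stands: removal is possible, not established. It does not settle the matter, because low quality, motion and missing sequences already cover much technical failure, no sentence keeps men with adequate lesion-free scans, and lesion-based registration makes their removal plausible.

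A reader might also infer that accuracy as a whole is overstated. The protocol names AUC, decision curves and clinical impact curves, and does not name sensitivity. As the working shows, the AUC bias has no fixed sign. That objection stands in full.

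Three smaller points also stand:
- Consecutive enrolment is always subject to exclusions, so there is a tension with the stated population but no formal contradiction. Likewise, the background's mention of "potential overdiagnosis or underdiagnosis" is tied to microscopic heterogeneity and does not refer to MRI-invisible cancer.
- The protocol does not say whether exclusion 2 applies to the international public dataset, so the point is confined to the study's own cohorts.
- Men spared biopsy after a negative MRI are outside this population whatever exclusion 2 says.

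Finally, registration needs a lesion to align, so requiring one for that step and for lesion-level training is defensible. This does not justify the same requirement in validation.

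**Conclusion.** The point holds as a defect of wording with a real selection risk. Exclusion 2 contains an undefined, outcome-related ground that can narrow the study's own training and validation cohorts to men with visible lesions, while the objectives concern biopsy decisions in men with suspected cancer.

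If it is applied that way, sensitivity is overstated provided the model detects invisible csPCa less well (0.92 reported against 0.81 to 0.90), specificity may be understated, and AUC is biased in an unknown direction. These sizes rest wholly on assumed inputs. The documents do not support a claim that every MRI-negative man is excluded, that the AUC is inflated, or that the public-dataset validation is affected. Eligibility is fixed in the protocol, so this should be corrected there; a later analysis plan cannot recover men who were never entered.

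**What to change.** Strike the last three words of exclusion 2, the unrecognizable-lesion ground, so that it covers technical image failure only (motion artifact, missing sequences). State that image quality is judged without knowledge of pathology.

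State that men with adequate images and no recognizable lesion on mpMRI, TRUS or both remain in the validation cohorts and are scored at patient level. A recognizable lesion may still be required for lesion-level registration and training. Say whether exclusion 2 applies to the public dataset.

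Report the number excluded by reason and by modality, with their csPCa rate, so that readers can judge the remaining selection.

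The text change is small. The practical costs are a patient-level score for lesion-free scans, which the registration-based pipeline must be able to produce, and a reported sensitivity that may be lower. If only technical failure was ever intended, the change removes the ambiguity without altering the intended population.

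### Complete clinical data is made a condition of entry, so men with usable imaging and pathology can be dropped for one missing routine item

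*Protocol*

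**What the plan says.** Protocol section 4 describes the population as "Consecutive male subjects aged 40 to 90 years with suspected prostate cancer who complete standard preoperative mpMRI and TRUS examinations" and who go on to biopsy or prostatectomy with a full pathological diagnosis. Its next sentence limits the population to "retrospective historical cases and prospective newly enrolled cases with complete clinical, imaging and pathological data". Exclusion 5 repeats the condition by removing "Subjects with incomplete clinical, imaging or pathological data".

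Other criteria in section 4 already cover imaging and pathology. Inclusion 3 requires both imaging examinations, exclusion 2 removes "Subjects with incomplete or low-quality mpMRI or TRUS images with motion artifacts, missing sequences or unrecognizable lesions", and inclusion 4 requires "Subjects with complete postoperative pathological results including Gleason score and ISUP grading".

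Section 5 states what the clinical data are: "Collected clinical data include age, BMI, PSA-related serological indicators and PI-RADS v2.1 scoring results". It names no core set and no tolerated level of missingness. Section 3 gives the source: "Only routine standard-of-care clinical data, imaging data and pathological data are collected and analyzed", from a retrospective and a prospective cohort.

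**The concern.** Because imaging and pathology are covered elsewhere, what exclusion 5 mainly adds is a requirement for complete clinical data. Taken with section 5, it lets a man be refused entry over a missing BMI or PSA-related value although the images and the reference standard are all there.

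In routine records, whether an item was measured and written down can depend on the centre, the period and how suspicious the clinician was. Suspicion is related to the outcome, so the rule can select on something related to clinically significant cancer, and can do so differently by cohort and site. Three things are exposed:

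- the primary AUC (section 7);
- the generalization claim (secondary objective 2), which rests on comparing data from different sources;
- net benefit and biopsy strategy (secondary objectives 3 and 4), which depend directly on prevalence.

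This is not a matter that the protocol may leave to the SAP. An analysis plan can choose how to handle missing values among enrolled men, but it cannot bring back men who were never eligible.

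**Working it through.** The protocol states no missingness rate, prevalence or expected AUC, so it has no figure to reproduce. Everything below except the 3000 is an assumption used to gauge size.

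**1. How many men the rule could remove.** Of the listed items, age is fixed by inclusion 1, which leaves three: BMI, PSA-related indicators and PI-RADS. With each independently missing at rate m, the share lost is 1 − (1 − m)^3.

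- m = 5%: 1 − 0.95^3 = 14.3%, or 428 per 3000 otherwise eligible men.
- m = 10%: 1 − 0.90^3 = 27.1%, or 813 per 3000.

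Sensitivity at the same 5–10% rates:

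| Assumption | Share lost |
|---|---|
| The same men lack every item | 5–10% (150–300 per 3000) |
| PI-RADS always available, two items left | 9.8–19.0% |
| Three items, independent | 14.3–27.1% |
| Four items, independent (age counted) | 18.5–34.4% |

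The 3000 is planned enrollment, so these losses raise the number to be screened and do not shrink the study. With three items the need is 3000/0.857 ≈ 3500 to 3000/0.729 ≈ 4116 otherwise eligible men.

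**2. What could happen to the AUC.** Both simulations used 1,000,000 men, 40% prevalence and a binormal score with true AUC 0.80.

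*Missingness tied to a suspicion score correlated with the model score* (20–40% missing in the affected band, 5% elsewhere):

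- affected band = outer 60% (clear-cut men): complete-case AUC 0.796 to 0.790;
- affected band = middle 40% (equivocal men): 0.803 to 0.808.

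A rerun gave closely similar values with the correlation set at about 0.7. Weaker correlation gives smaller shifts.

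*Missingness tied directly to the model score*, a harsher assumption:

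| Mechanism | Men retained | AUC | Prevalence |
|---|---|---|---|
| Completely at random, 20% | 80% | 0.80 | 40% |
| Equivocal men 30% vs 10% | 82.5% | 0.811 | 40.3% |
| Equivocal men 50% vs 10% | 75.0% | 0.823 | 40.6% |
| Low-risk men 30% vs 10% | 79.9% | 0.797 | 42.7% |
| Low-risk men 50% vs 10% | 69.8% | 0.789 | 46.1% |

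**3. Comparison with sampling error.** Hanley–McNeil at AUC A = 0.80, with Q1 = A/(2 − A) = 0.667, Q2 = 2A²/(1 + A) = 0.711 and A² = 0.64:

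- n = 3000 (1200 cases, 1800 non-cases): variance = [0.16 + 1199 × 0.0267 + 1799 × 0.0711]/(1200 × 1800) = 0.0000741; SE 0.0086; 95% half-width 1.96 × 0.0086 = 0.017.
- n = 1000 (an assumed validation-set size): SE 0.0149; half-width 0.029.

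**4. Net benefit.** At an illustrative 10% threshold, biopsying everyone has net benefit p − (1 − p)/9, where p is prevalence.

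- p = 0.400: 0.400 − 0.600/9 = 0.333
- p = 0.427: 0.427 − 0.573/9 = 0.363
- p = 0.461: 0.461 − 0.539/9 = 0.401

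This is the reference curve, not the model's advantage over it. It shows that decision curves can shift through selection alone.

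**The case against.** Several points on the other side are sound.

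- **Consecutive enrollment.** A reader might infer that the rule contradicts it. It does not. The population description openly adds the completeness condition, so the word can only mean consecutive among men with complete records. The rule narrows the claim without making it false.
- **Fully worked-up men.** A reader might blame exclusion 5 for the whole restriction of the AUC to such men. Most of that restriction comes from inclusions 3 and 4 and exclusion 2, which protect the index images and the reference standard and should stay. Exclusion 5 adds only the clinical-item margin.
- **Proof of bias.** None is available. The documents give no missingness rate or mechanism. With data missing completely at random the AUC is unaffected, and a shift of 0.01 lies inside the sampling error even at n = 3000.
- **The loss figures.** They rest on assumed rates and independence. PI-RADS is a weak candidate for missingness, since every eligible man has an adequate mpMRI from which it could be scored.
- **Undefined term.** The protocol does not define incomplete clinical data. That every item in section 5 is required comes from reading sections 4 and 5 together, and operational documents may set a shorter list.
- **Model inputs.** No section says that BMI or PSA enters the model; sections 2 and 6 describe registered imaging and digital pathology.

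The last two points limit the claim but do not remove it. An undefined term in an exclusion criterion leaves each centre to decide, which is itself a route to selection that differs by site. And if clinical items are not model inputs, there is less reason to exclude a man for lacking one.

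**Conclusion.** The point holds as a concern about selection and applicability. Completeness of clinical data is written as an eligibility condition for both cohorts, it is avoidable, and a later analysis plan cannot undo it.

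Its size is uncertain. Under assumed independent missingness of 5–10% in three items, 14–27% of otherwise eligible men are lost, and as few as 5–10% if missing items cluster in the same men. The AUC shift is about 0.01 in either direction under moderate selective missingness, about 0.02 only under the harshest scenario examined, and zero if data are missing completely at random. Prevalence, and with it net benefit, can move more: from an assumed 40% to 43–46% if low-risk men are more often incomplete.

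A reader might infer that the reported AUC or the generalization claim will be biased. The documents do not support that; they support only that the rule can select the sample, and differently by centre or cohort. This is a cheap improvement, not a fatal flaw.

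**What to change.** In section 4, limit exclusion 5, and the matching sentence in the population description, to men without reference-standard pathology or without a required imaging modality. Keep men whose only gap is a clinical item.

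If any clinical item enters the model, impute it with a procedure fitted in the training data only and applied unchanged to the validation data, and give the complete-case AUC as a sensitivity analysis. If none enters the model, no imputation is needed for the primary AUC.

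In either case, report the number of men excluded, the reasons, and the missing clinical items, by centre and by cohort.

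The cost is a short amendment to two sentences, modest extra analysis and, where clinical items are used, reliance on an imputation model for a few covariates. No image or pathology result is imputed. The study is recruiting, so an early change keeps prospective men who would otherwise be turned away, and retrospective cases can be re-screened.
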